8.1 Sample Size

A total of 24 healthy adult male or female volunteers will be included in study Part 1. Only 16 subjects who completed study Part 1 will be included in study Part 2. In order to minimize potential PK variability, elderly (more than 65 years old subjects) will be not included in study Part 2. These 16 subjects will be selected according to their order of enrolment in the study, provided their consent to continue the study, they follow the study restrictions and they still meet study criteria. Subjects numbers are judged adequate to achieve the study objectives.

For study Part 1 only, an effort will be made to include to the extent possible, subjects of the following age groups:

- ≥ 65 and ≤ 70 years of age;
- ≥ 70 and ≤ 75 years of age.

8.2 Inclusion Criteria

Subjects enrolled in this study will be members of the community at large. The recruitment advertisements may use various media types (e.g., radio, newspaper, the clinical site Web site and volunteer database). Subjects must meet all of the following criteria to be included in the study:

- 1) Normal healthy male or female volunteers, non-smokers (no use of tobacco products within 3 months prior to screening), ≥ 18 and ≤ 75 years of age, with BMI > 18.5 and < 30.0 kg/m² and body weight ≥ 50.0 kg for males and ≥ 45.0 kg for females.
- 2) Healthy as defined by:
 - a) the absence of clinically significant illness and surgery within 4 weeks prior to dosing. Subjects vomiting within 24 hours predose will be carefully evaluated for upcoming illness/disease. Inclusion pre-dosing is at the discretion of the Investigator.
 - b) the absence of clinically significant history of neurological, endocrine, cardiovascular, respiratory, hematological, immunological, psychiatric, gastrointestinal, renal, hepatic, and metabolic disease as determined by the Investigator.
- 3) Females of childbearing potential who are sexually active with a male partner must be willing to use one of the following acceptable contraceptive methods throughout the study and for 30 days after the last study drug administration:
 - a) intra-uterine contraceptive device without hormone release system placed at least 4 weeks prior to study drug administration;
 - b) male condom with intravaginally applied spermicide starting at least 21 days prior to study drug administration;
 - c) sterile male partner (vasectomized since at least 6 months).
- 4) Capable of consent

8.3 Exclusion Criteria

Subjects to whom any of the following applies will be excluded from the study:

- 1) Any clinically significant abnormality at physical examination, clinically significant abnormal laboratory test results or positive test for hepatitis B, hepatitis C, or HIV found during medical screening.
- 2) Positive urine drug screen or urine cotinine test at screening.
- 3) History of allergic reactions to resveratrol, polyphenols, other related drugs, or to any excipient in the formulation.
- 4) Positive pregnancy test at screening.
- 5) Breast-feeding subject.
- 6) Clinically significant ECG abnormalities or vital sign abnormalities (systolic blood pressure lower than 90 or over 140 mmHg, diastolic blood pressure lower than 50 or over 90 mmHg, or heart rate less than 50 or over 100 bpm) at screening.
- 7) History of significant alcohol abuse within 1 year prior to screening or regular use of alcohol within 6 months prior to the screening visit (more than 14 units of alcohol per week [1 unit = 150 mL of wine, 360 mL of beer, or 45 mL of 40% alcohol]).
- 8) History of significant drug abuse within 1 year prior to screening or use of soft drugs (such as marijuana) within 3 months prior to the screening visit or hard drugs (such as cocaine, phencyclidine [PCP], crack, opioid derivatives including heroin, and amphetamine derivatives) within 1 year prior to screening.
- 9) Use of resveratrol for a medical condition or in the context of another clinical trial within a period of 30 days prior to the first dosing.
- 10) Participation in a clinical research study involving the administration of an investigational or marketed drug or device within 30 days prior to the first dosing, administration of a biological product in the context of a clinical research study within 90 days prior to the first dosing, or concomitant participation in an investigational study involving no drug or device administration.
- 11) Use of medications for the timeframes specified below, with the exception of medications exempted by the Investigator on a case-by-case basis because they are judged unlikely to affect the PK profile of the study drug or subject safety (e.g., topical drug products without significant systemic absorption:
 - a) prescription medication within 14 days prior to the first dosing;
 - b) over-the-counter products and natural health products (including herbal remedies, homeopathic and traditional medicines, probiotics, food supplements such as vitamins, minerals, amino acids, essential fatty acids, and protein supplements used in sports) within 14 days prior to the first dosing, with the exception of the occasional use of acetaminophen (up to 2 g daily);

- c) use of any drugs known to induce or inhibit hepatic drug metabolism, including St. John's wort, within 30 days prior to the first study drug administration;
 - d) depot injection or an implant of any drug within 3 months prior to the first dosing.
- 12) Donation of plasma within 7 days prior to dosing. Donation or loss of blood (excluding volume drawn at screening) of 50 mL to 499 mL of blood within 30 days, or more than 499 mL within 56 days prior to the first dosing.
- 13) Any reason which, in the opinion of the Investigator, would prevent the subject from participating in the study.

9. Clinical Procedures

Unless otherwise specified, procedures, data collection and evaluation will be conducted as per the clinical site SOPs.

9.1 Screening Procedures

Subject screening procedures will be performed within 28 days preceding administration of study medication. Subjects must provide written informed consent prior to initiation of any screening procedures. The consent to perform some general screening procedures may be obtained on a consent document other than the Informed Consent Form (ICF) specific to this study, and therefore, some screening test results could be obtained before signature of the ICF specific to this study. The study-specific ICF must be signed and dated by the subject before participation to study-specific procedures.

Screening procedures will include: demographic data, medical and medication histories, physical examination, body measurements, ECG (12-lead), vital signs (blood pressure, heart rate, respiratory rate, and oral temperature), hematology, biochemistry, coagulation, serology (HIV, hepatitis B and C tests), urinalysis, urine cotinine test, urine pregnancy test, and urine drug screen.

For eligibility purposes, abnormal laboratory or vital signs results may be repeated once if abnormal result is observed at the initial reading. Moreover, abnormalities found in the ECG may need to be confirmed by repeated measurements. In the event that the participation of a subject in the study is delayed and some screening procedures had been performed outside the prescribed screening window, outdated screening procedures can be repeated.

9.2 Confinements, Visits, and Washout

For each period, subjects will be confined from Day -1 until after the 32-hour post-dose blood draw.

There will be a washout of 14 days or more between doses. The washout period may be increased for logistical considerations. Participation of each subject in this study should last approximately 1 month (for subjects participating in study Part 1 only) and 1.5 months (for subjects participating in both study parts).

9.3 Study Medication

- Treatment A (Period 1):** JOTROL (resveratrol) 100 mg oral gelcap (Jupiter Oprhan Therapeutics, USA) given as 2 x 100 mg gelcaps under fasting conditions, total resveratrol dose: 200 mg
- Treatment B (Period 2):** JOTROL (resveratrol) 100 mg oral gelcap (Jupiter Oprhan Therapeutics, USA) given as 5 x 100 mg gelcaps under fasting conditions, total resveratrol dose: 500 mg
- Treatment C (Period 3):** JOTROL (resveratrol) 100 mg oral gelcap (Jupiter Oprhan Therapeutics, USA) given as 10 x 100 mg gelcaps under fasting conditions, total resveratrol dose: 1000 mg
- Treatment D (Period 4):** JOTROL (resveratrol) 100 mg oral gelcap (Jupiter Oprhan Therapeutics, USA) given as 10 x 100 mg gelcaps under fed conditions, total resveratrol dose: 1000 mg

Targeted doses will be achieved with multiple JOTROL' gelcaps containing 100 mg of resveratrol. For Periods 2 and 3, JOTROL's doses to be administered will be reassessed when safety, tolerability, and PK data analysis are available. The same dose is planned to be administered in Periods 3 and 4. However, if the exposure is higher than expected in Period 3, the dose administered could be lower in Period 4, in order to keep AUC exposures lower than 2.1 $\mu\text{g}\cdot\text{hr}/\text{mL}$, as specified in section 7.2.

9.4 Drug Supplies and Accountability

It is the responsibility of the Sponsor to ensure that study medication provided for this study are manufactured under Good Manufacturing Practices (GMP) and are suitable for human use. The Sponsor is responsible to ship a sufficient amount of dosage units to allow the clinical site to maintain an appropriate sampling for the study.

Study medication will be stored at the clinical site as per applicable requirements. The medications will be stored in a locked, environmentally-controlled medication room with restricted access. Container(s) will bear a label containing at least the name of the study drug, lot and/or batch number, and manufacturing and/or expiry/retest date.

Individual doses for each subject will be dispensed at the clinical site, as per appropriate SOP. Individual doses will be dispensed in appropriate envelopes/containers indicated with at least the project number and the subject number/spare number.

All study drug received at the site will be inventoried and accounted for throughout the study and the result recorded in the drug accountability/retention record according to the clinical site appropriate SOP.

9.5 Drug Administration

Study medication will be administered to each subject with approximately 240 mL of water and a hand and mouth check will be performed to ensure consumption of the medication. Additional water may be provided if needed.

Study Part 1 (Periods 1, 2, and 3): All subjects will be sequentially dosed in an ascending manner with at least 14 days between the last dosing and the subsequent nominal dose level which will be calculated based on observed safety, tolerability, and PK results. Subjects will receive a single oral dose of JOTROL gelcaps under fasting conditions using the following nominal dosage levels:

Study period	Planned dose levels of JOTROL
1	200 mg (given as 2 x 100 mg gelcaps), total dose of resveratrol: 200 mg
2	500 mg (given as 5 x 100 mg gelcaps), total dose of resveratrol: 500 mg
3	1000 mg (as 10 x 100 mg gelcaps), total dose of resveratrol: 1000 mg

For Periods 2 and 3, JOTROL's doses to be administered will be reassessed when safety, tolerability, and PK data analysis are available. Adjustment to the currently outlined doses and/or dosing regimen may be necessary, but the dose to be administered in Period 2 or 3 will not exceed the one currently outlined in the protocol.

Time of dosing will be set equal to the time when the first gelcap is administered to the subject. The complete dosing procedure must be completed within 3 minutes.

Following completion of each dose level, PK, safety, tolerability data will be evaluated by a Safety Committee **and a DSMB** before proceeding to the next dose.

The same JOTROL dose will be administered in Periods 3 and 4.

Study Part 2 (Period 4): Only 16 subjects who completed study Part 1 will receive the highest dose of JOTROL tested during study Part 1, as a single oral dose of JOTROL gelcaps under fed conditions. In order to minimize potential PK variability, elderly (more than 65 years old subjects) will be not included in study Part 2. However, depending on safety and tolerability as well as on available PK data from Part 1 (in order to keep AUC exposures lower than 2.1 $\mu\text{g}\cdot\text{hr}/\text{mL}$, as specified in section 7.2.), the dose to be used during study Part 2 may be reduced.

9.6 Study Restrictions

9.6.1 Food and Fluids

Study Part 1 (Periods 1, 2, and 3): No food will be allowed from at least 10 hours before dosing until at least 4 hours after dosing.

Study Part 2 (Period 4): After a supervised fast of at least 11 hours, subjects will be served a critical, high-fat, high-calorie meal of approximately 800 to 1000 calories (approximately 50% of total caloric content of the meal derived from fat). This test meal should derive approximately 150, 250, and 500-600 calories from protein, carbohydrate, and fat, respectively. The meal will consist of two eggs fried in butter, two slices of toast with butter, two strips of bacon, 120 g of hash brown potatoes, and 240 mL of whole milk. Subjects will be informed to start their meal as soon as it is served and to complete it in 30 minutes or less. Subjects will be informed that they should eat the entire meal. Drug administration will occur 30 ± 1 minutes after the meal has been started. Subjects will fast for not less than 4 hours after drug administration.

Meals will be standardized and similar in composition between periods.

Except for fluids provided with the critical breakfast (study Part 2 only) and water given with study medication, no fluids will be allowed from 1 hour before dosing until 1 hour post-dose. Water will be provided *ad libitum* at all other times.

In addition, subjects will be required to abstain from:

- food containing poppy seeds within 24 hours prior to admission;
- food or beverages containing xanthine derivatives or xanthine-related compounds or energy drinks from 48 hours prior to dosing until after the last PK blood sample collection of each period;
- food or beverages containing grapefruit, starfruit, pomegranate, pineapple, or pomelo from 7 days prior to dosing until after the last PK blood sample collection of each period;
- foods rich in resveratrol (e.g. grapes, peanuts and their derived-products including wines and juices) from 7 days pre-dose until after the last PK blood sample collection of each period.

9.6.2 Tobacco, Alcohol, and Illicit Drugs

Subjects will be required to abstain from using soft or hard drugs or any tobacco products from screening and throughout the study.

Consumption of alcohol-based products will be prohibited from 24 hours prior to admission until after the last PK blood sample collection of each period.

9.6.3 Concomitant Medications

Subjects will be required to avoid using prescription and over-the-counter medications for the period of time specified in exclusion criterion 11) and throughout the study. Subjects will be required to avoid using natural health products (including herbal remedies, homeopathic and traditional medicines, probiotics, food supplements such as vitamins, minerals, amino acids, essential fatty acids, and protein supplements used in sports) from 14 days prior to dosing until after the last PK blood sample collection of each period.

No concomitant medications are allowed during the study, with the exception of one(s) required for the medical management of an adverse event, medications exempted by the Investigator on a case-by-case basis that are judged unlikely to affect the pharmacokinetic profile of the study drug or subject safety (e.g., topical drug products without significant systemic absorption) and occasional use of acetaminophen.

All medications taken by subjects after screening until the last study day will be documented as concomitant medications. Any concomitant medication use, other than the allowed medications stated above, will be reviewed and evaluated on a case-by-case basis by the Investigator to determine if they affect a subject's eligibility or continued participation in the study, or for potential impact on the study results.

9.6.4 Posture and Physical Activity

Subjects will be allowed to engage in normal activity but will avoid lying down or sleeping, unless medically necessary or procedurally required, for 2 hours (study Part 1) and 4 hours (study Part 2) after drug administration. Vigorous activity will be prohibited at all times during the confinement.

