
Study Restrictions:
	
Subjects will be asked to refrain from using products that may potentially affect their safety and/or the PK profile of the study drug. Main study restrictions include:
 
 • prescription medication from 14 days prior to the first dosing until after the last PK blood sample collection of the study ; • over-the-counter products from 14 days prior to the first dosing until after the last PK blood sample collection of the study; • any drugs known to be strong inducer or inhibitor of hepatic drug metabolism, including St. John's wort, within 30 days prior to the first dosing until after the last PK blood sample collection of the study; • natural health products from 14 days pre-dose until after the last pharmacokinetic blood sample collection of each period; • food containing poppy seeds within 24 hours prior to admission; • food or beverages containing xanthine derivatives or xanthine-related compounds or energy drinks from 48 hours pre-dose until after the last PK blood sample collection of each period;

	
 • food or beverages containing grapefruit, starfruit, pomegranate, pineapple, or pomelo from 7 days pre-dose until after the last PK blood sample collection of each period; • foods rich in resveratrol (e.g. grapes, peanuts and their products including juices and wines) from 7 days pre-dose until after the last PK blood sample collection of each period; • alcohol-based products from 24 hours prior to admission until after the last PK blood sample collection of each period. 
Subjects will be allowed to engage in normal activity but will avoid lying down or sleeping, unless medically necessary or procedurally required, for 2 hours (study Part 1) and 4 hours (study Part 2) after study drug administration.

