12.3 Statistical Analyses

Demographic parameters will be summarized descriptively. TEAEs will be summarized descriptively by treatment for all subjects who were dosed (safety population). No inferential statistical analysis of safety data is planned.

Individual and mean plasma concentration versus time curves will be presented for both linear and semi-log scales. Descriptive statistics (arithmetic and geometric means, standard deviation [SD], coefficient of variation [CV%], minimum [Min], maximum [Max], and median) of the plasma concentrations versus time will be presented as well for the pharmacokinetic parameters.

A Statistical Analysis Plan (SAP) will be prepared after completion of the final protocol.

Safety and tolerability:

TEAEs will be tabulated by treatment. Changes from screening to study exit values in vital signs, ECG, and clinical laboratory parameters will be evaluated. Safety and tolerability data will be reported using descriptive statistics. Results of vital signs, ECG, and clinical laboratory parameters, urine drug screens, clinical laboratory tests, pregnancy tests, alcohol breath test, and urine cotinine test will be listed.

PK

- Plasma PK:

For all analytes, summary statistics will be used to describe the PK profile for each dose level under fasting conditions (Periods 1, 2, and 3) and under fed conditions (Period 4).

Dose proportionality analysis for AUC_{0-t} , AUC_{0-inf} and C_{max} will be performed (using the power model with mixed procedure from SAS[®]) considering data under fasting conditions (Periods 1, 2, and 3).

For evaluation of the food-effect, PK data (ln-transformed AUC_{0-t} , AUC_{0-inf} , C_{max} and untransformed T_{max}) reported under fed conditions (Period 4) and under fasting conditions (for the same dose level) will be compared using ANOVA from SAS[®]. The ratio (fed/fasting) and 90% geometric confidence interval will also be calculated for AUC_{0-t} , AUC_{0-inf} and C_{max} .

All inferential statistical analyses will be interpreted in an exploratory sense only at an alpha level of 5% for statistical significance.

Additional statistical analysis may be performed.

- Urine PK:

Summary statistics will be used to describe urinary excretion of resveratrol, resveratrol-3-glucuronide, resveratrol-4'-glucuronide, and resveratrol-3-sulfate.

Additional statistical analysis may be performed.

13. Regulatory Considerations and Quality Assurance

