### 10.5.4 Food-Effect assessment

For evaluation of the food-effect, PK data (ln-transformed  $AUC_{0-t}$ ,  $AUC_{0-inf}$ ,  $C_{max}$  and untransformed  $T_{max}$ ) reported under fed conditions (Period 4) and under fasting conditions (for the same dose level) will be compared using ANOVA from SAS®. The ratio (fed/fasting) and 90% geometric confidence interval will also be calculated for  $AUC_{0-t}$ ,  $AUC_{0-inf}$  and  $C_{max}$ .

If 90% CI for  $AUC_{0-t}$ ,  $AUC_{0-inf}$  and  $C_{max}$  are within 80.00% to 125.00% then no food effect will be concluded.

For all analytes, using GLM procedure in SAS, ANOVA will be performed on ln-transformed  $AUC_{0-t}$ ,  $AUC_{0-inf}$  and  $C_{max}$  at the alpha level of 0.05. The model will include Treatment as fixed effect and Subject as a random effect. Inter- and intra-subject coefficient of variation will be estimated. The ratio of geometric means and 90% confidence interval for the ratio of geometric means, based on least-squares means from the ANOVA of the ln-transformed data, will be calculated for  $AUC_{0-t}$ ,  $AUC_{0-inf}$ , and  $C_{max}$ .

```

SAS® codes for ANOVA: fed vs. fasting
PROC GLM data=basepk;
CLASS TREATMENT SUBJECT;
MODEL VAR = TREATMENT SUBJECT;
RANDOM SUBJECT;
LSMEANS TREATMENT / cl pdiff alpha=0.1;
ESTIMATE 'fed - fasting' TRT 1 -1/cl alpha=0.1;

run;
```

---

Additional statistical analysis may be performed.

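### The fasting and fed periods have different posture windows (2 h versus 4 h), so the food-effect contrast carries a small, avoidable difference that the analysis cannot separate from the meal

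*Protocol*

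**What the plan says.** Protocol 9.6.4 says that subjects "will avoid lying down or sleeping, unless medically necessary or procedurally required", and sets the duration "for 2 hours (study Part 1) and 4 hours (study Part 2) after drug administration". The synopsis, under Study Restrictions, has the same split: "for 2 hours (study Part 1) and 4 hours (study Part 2) after study drug administration". The two places agree, so the difference looks intended. Neither explains it, and the SAP does not mention posture.

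Part 1 (Periods 1 to 3) is fasting and Part 2 (Period 4) is fed. Protocol 9.5 plans that "The same JOTROL dose will be administered in Periods 3 and 4", which makes Period 3 the fasting reference. The same section allows a lower dose in Period 4, but any fasting reference would still come from Part 1.

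SAP 10.5.4 takes PK data "reported under fed conditions (Period 4) and under fasting conditions (for the same dose level) will be compared using ANOVA". On the model it says: "The model will include Treatment as fixed effect and Subject as a random effect". If the 90% intervals for AUC0-t, AUC0-inf and Cmax "are within 80.00% to 125.00% then no food effect will be concluded". The ANOVA is run for all analytes, and SAP section 5 lists AUC and Cmax of the three conjugates among the primary parameters.

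**The concern.** A fed/fasting ratio is read as the effect of the meal, so the two conditions should otherwise be alike. Protocol 9.6.1 takes care of this elsewhere: both conditions have a post-dose fast of at least 4 h, the same fluid restriction around dosing apart from the breakfast fluids, and standardized meals between periods. The posture window is an exception. From 2 to 4 h a subject may lie down in Period 3, while the same subject may not in Period 4.

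If posture affects concentrations in that interval, the effect goes into the food estimate. The food effect is one of the two stated study objectives.

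**Working it through.** The plan states no posture effect and no power calculation for Part 2, so there is no figure to reproduce. Three checks were made.

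**1. Can the analysis separate posture from food?** Take 16 subjects (Protocol 8.1), each with one fasting and one fed record, which gives 32 rows.

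| Model | Columns | Rank |
|---|---|---|
| Subject + Food | 17 | 17 |
| + posture rule | 18 | 17 |
| + period | 19 | 17 |

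The posture column equals the food column, so it adds nothing to the rank. The rule is fully aliased with food. Period is aliased in the same way, because the fed dose always comes last.

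**2. What falls inside the gap?** Of the 17 sampling times in Protocol 9.7.1, only 3 h and 4 h lie in it. The 2 h sample closes the matched window, and the 5 h and 6 h samples come after both windows end, although an earlier effect could carry over into them. Published fasting data on unmodified resveratrol (Protocol Table 1, 1 g) give these times to peak:

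| Analyte | Median Tmax (range), h |
|---|---|
| Resveratrol | 0.759 (0.5-4.0) |
| Glucuronide 1 | 2.250 (1.0-6.0) |
| Glucuronide 2 | 1.750 (1.0-5.1) |
| 3-Sulfate | 2.000 (1.0-5.0) |

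Protocol 4.3.2 gives 0.8-1.5 h for the parent at lower doses. Fasting parent Cmax is therefore usually set while the rules still match. AUC, late-peaking profiles and the conjugates are more open to the difference.

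**3. How far could AUC move?** This is an illustration on assumptions, not an estimate. Assume a one-compartment oral curve, C(t) proportional to exp(-ke·t) - exp(-ka·t), with ke = ln 2 / half-life and ka solved from Tmax = ln(ka/ke)/(ka - ke). Take Tmax from 0.76 to 2.5 h, and half-life from 2.85 h (Table 1, 0.5 g, one participant) to 8.87 h (1 g). Let s = AUC2-4 / AUC0-32.

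| Tmax (h) | s, half-life 2.85 h | s, half-life 8.87 h |
|---|---|---|
| 0.76 | 0.253 | 0.137 |
| 1.5 | 0.275 | 0.140 |
| 2.0 | 0.273 | 0.140 |
| 2.5 | 0.256 | 0.138 |

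The gap thus holds about 14% to 28% of AUC0-32. If posture multiplies fasting concentrations in the gap by (1 + x), a true ratio of 100% is read as 100/(1 + s·x). With s from 0.137 to 0.275 (ratios for the rises use unrounded s):

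- x = +5%: 98.6% to 99.3%
- x = +10%: 97.3% to 98.7%
- x = +20%: 94.8% to 97.3%
- x = +30%: 92.4% to 96.1%

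The direction is unknown, so the reverse also applies:

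- x = -10%: 100/(1 - 0.0137) = 101.4% to 100/(1 - 0.0275) = 102.8%
- x = -30%: 100/(1 - 0.0411) = 104.3% to 100/(1 - 0.0825) = 109.0%

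All of these stay inside 80-125%. Only a result already near a limit would be sensitive. At x = +10% and the larger share, a lower confidence limit between 80.00% and 80/0.973 = 82.2% would be read as below 80.00%.

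**The case against.** The best defence is that the split is deliberate and reasonable. The same 2 h/4 h pattern governs how long the investigator stays on site (Protocol 9.8), and the vomiting window is also longer in Part 2 (3 h versus 7 h, Protocol 9.11). Protocol 4.3.2 reports that a high-fat meal delays the peak, so a longer window when fed would fit a later absorption phase. This is plausible, but the documents do not say so, and it would not make the two conditions comparable.

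Other parts of the defence stand and limit the weight of the point:

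- The rule sets a minimum time without lying down. It does not send anyone to bed at 2 h. Dosing appears to be in the morning, with blood draws at 3 h and 4 h and, in Part 1, a requested void just before 4 h. Actual posture may differ little.
- Neither document says why posture is restricted or that posture alters resveratrol exposure. A link to absorption is an assumption.
- Table 1 describes unmodified drug, not the micellar JOTROL formulation.
- Protocol 12.3 limits the claim: "All inferential statistical analyses will be interpreted in an exploratory sense only at an alpha level of 5% for statistical significance".

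A reader might infer from the conjugate medians near 2 h that about half of those profiles have absorption exposed to the posture difference. The documents do not support that, because conjugate peaks also reflect formation and elimination. Nor do they support applying a posture effect to Cmax in every fasting profile, since the first 2 h are matched.

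**Conclusion.** The point holds as a minor, avoidable design difference. The posture rule changes together with the meal, no reason is given, and no analysis of these data can separate the two. It does not follow that the food-effect result would be biased to a degree that matters, or that a conclusion of no food effect would be unsafe; a reader might infer either, but the documents give no posture effect, no direction, and no evidence that subjects would behave differently. On the illustrative assumptions (a one-compartment curve, Table 1 kinetics carried over to JOTROL, an effect confined to 2-4 h), a 10% change in the gap moves the AUC ratio by about 1% to 3%, and a 30% rise moves it by about 4% to 8%. It is worth correcting because the correction is cheap, not because the expected harm is large.

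**What to change.** In Protocol 9.6.4 and in the synopsis under Study Restrictions, set one posture window for all four periods, for example by extending the Part 1 window to match Part 2. Keep the present exception for medical or procedural need. What matters is that the windows match; the documents give no basis for preferring a particular length.

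Do not change Period 3 alone. That would make the rule differ within Periods 1 to 3, which feed the dose-proportionality model in SAP 10.5.2 and are now uniform.

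The change is one number in two places, and subjects are already confined. The cost is more time upright in the fasting periods if the longer window is used, including for subjects over 65 who do not enter Part 2. Food would remain aliased with period order. If Part 1 has already been dosed, or if the sponsor wishes to keep two windows, state the reason and report the difference as a limitation of the fed/fasting comparison.
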